Cover letter

Title: Comparison Between the Dentapen and Vibraject: a Randomized Clinical Study on the Administration of Local Anaesthesia in Adult Patients.

Date: January 14, 2025

STUDY PROTOCOL

Ethical Approval

The study was conducted in compliance with the Helsinki Declaration. Each participant in this study was given a thorough explanation of the procedures and signed a consent form attesting to their comprehension. Ethical approval was obtained from the research centre at Riyadh Elm University prior to conducting this research (FPGRP/2023/715/906/892). The informed consent was obtained from the participants who volunteered in this research.

Outcome Measurement

In this study, each patient received two injections in both sides of the maxilla buccally next to the first molar, with the type of injection being randomly assigned. Immediately following each local anaesthesia injection, patients were requested to rate their pain intensity using the Visual Analogue Scale. Additionally, heart rate measurements were taken before and after each injection to monitor physiological responses to pain.

After both injections were completed, patients were asked to indicate their preferred injection. This preference was based on their subjective experience and was recorded by selecting the injection number (either the first or second) in the order they were administered for each patient. This method aimed to provide insights into patient comfort and pain perception associated

Inclusion Criteria:

- Individuals classified under American Society of Anesthesiologists classes I and II, indicating a healthy or mild systemic disease status.
- Individuals aged from 18 up to 65 years, encompassing both male and female patients.

- Individuals who required local anesthetic injections bilaterally in the buccal side of the upper posterior teeth. These injections were necessary for various dental procedures, including restorative, endodontic, or prosthodontic treatments, and volunteers as well were to be administered across both sides of upper posterior teeth.
- Individuals must be in good health, not currently taking any medication, and have no contraindications to the use of local anesthesia.
- Individuals who have the ability to understand both oral and written instructions, ensuring effective communication and comprehension throughout the study.

Exclusion Criteria:

- Individuals with allergies to local anesthetics, this is to prevent adverse reactions.
- Pregnant or nursing women, this is to avoid any potential risks to their health or that of their infants.
- Individuals who were actively taking drugs that could alter pain perception or anxiety levels, such as nonsteroidal anti-inflammatory drugs, opioids, or antidepressants. This was to ensure that the study's findings on pain perception were not influenced by external substances
- Individuals with heavy alcohol consumption. .
- Patients with active pathologies at the injection site, this is to avoid complications and to ensure the accuracy of the study's results.
- Individuals who could not commit to the study's schedule or were unable to give informed consent. This ensured that all participants were fully aware of and agreeable to the study's procedures and requirements.
- Patients who required intravenous sedation for their dental procedures.

Sample Size

The study was designed with a carefully considered sample size to ensure statistical significance and reliability of the results. The sample size for the study was determined utilizing the G-power calculator, resulting in a decision to allocate 40 participants to each of the two groups, with each participant receiving two different injections, thereby evaluating 80 sites in total. This approach allowed for a comprehensive comparison between the two injection types, as each patient served as their control.

Study Design

The study commenced with an initial assessment to determine patient eligibility. Once eligibility was confirmed, the patient was scheduled for their first injection, during which their baseline heart rate was measured before any procedures. Following this, the patient received the first local anaesthesia injection using one of the two methods being compared in the study. After the injection was administered, the patient's heart rate was measured again to record any changes that may have occurred due to the injection then the patient will be asked to evaluate pain intensity with Visual Analogue Scale.

The patient then returned after one hour, and the patient's heart rate being recorded before the administration of local anaesthesia. For this second injection, the alternative injection method was used on the other side, ensuring that each patient experienced both types of injections. Following the second injection, the patient's heart rate was measured once more to capture the immediate physiological response and the patient will be asked again to evaluate pain intensity with Visual Analogue Scale.

[figure not shown]

Figure 1: Flow chart of the study

This study design is a split mouth clinical trial which allowed for a within-subjects comparison, where each patient's reaction to both injection methods could be directly compared. The heart rate measurements before and after each injection provided objective data on the physiological response to the injections.

Steps of the Experiment

The experimental protocol was meticulously structured to evaluate the efficacy and patient response to two different local anaesthetic delivery systems. The steps were as follows:

Step I: Before administering a local anaesthetic, the patient's heart rate was checked with a pulse oximeter (Beurer Finger Pulse Oximeter). The results were recorded.

Step II: Patients were randomly assigned to get the injection of local anaesthetic at their initial appointment either with the Dentapen system (ramp-up) or with Vibraject. To simplify the protocol, a 27-gauge needle was used for all dental injections with bevel side directly headed to the injected site.

Step III: In the next appointment, after one hour on a digital timer, the other technique was used for the same patients on the other side. Hence, each patient was given local anaesthesia twice, once with the Dentapen system (ramp-up mode) and once with Vibraject.

Step IV: Immediately after each local anaesthesia injection operation, the patient was asked to use the Visual Analogue Scale to score the intensity of reported pain.

Step V: After administering a local anaesthetic, the patient's heart rate was measured with a pulse oximeter (Beurer Finger Pulse Oximeter). The results were recorded.

Step VI: After both injections were administered to each patient, they were asked which injection they would prefer by selecting the injection number (first or second) according to their order for each patient.

Risk of Bias

To mitigate the risk of bias in this study, several blinding strategies were employed. All patients were blinded to the sequence in which the two anaesthetic techniques were administered. To further reduce variability and potential bias, all procedures were conducted by the same operator and he was trained to ensure all injections to go with same protocol and procedures. This approach eliminated any differences that could arise from operator technique, thus ensuring consistency across all injections. The individual responsible for performing the data analysis was also blinded to which technique was used for each patient. The blinding of the analyst was achieved by using coded data that concealed the identities and the specific techniques used for each patient, thereby maintaining the objectivity of the data interpretation.

Additionally, patients were asked to wear an eye mask during the injection process. The use of masks prevented patients from seeing the syringe and the method of injection being used, which could potentially influence their perception and subsequent reporting of pain. This step was crucial to maintain the integrity of the study's double-blind design, where neither the patients nor the individuals analyzing the data were aware of which technique was being used at any given point, thus preserving the study's methodological rigour.

Injection with the Dentapen® System (Ramp-up Mode)

According to the manufacturer's protocol, the Dentapen electronic syringe was used to administer local anaesthesia. To administer local anaesthesia, a cotton-tipped applicator with 20% benzocaine gel (Topox; Sultan Healthcare, Inc., York, PA) was applied topically after drying the mucosa and placed for 60 seconds using a digital timer. After 60 seconds, the target site was wiped with 2-inch cotton gauze before injecting 0.5 cartridge (0.9 mL) of 3% mepivacaine hydrochloride with no epinephrine (Henry Schein, Melville, NY) which was stored in room temperature. The

needle was advanced into the tissue until it was estimated to be over the root apex while remaining parallel to the tooth's long axis (needle placement). The Dentapen was activated after aspiration to deposit the solution at a medium rate (1 mL/60 s) using the ramp-up mode. Following cartridge deposition, the operator adjusted the participant to an upright seated position so that he or she could independently record his or her perceived pain on the Visual Analogue Scale.

Figure 2: Dentapen used in the study.

Injection with Vibraject

After drying the mucosa, a cotton-tipped applicator with a 20% benzocaine gel (Topox; Sultan Healthcare, Inc., York, PA) was placed for 60 seconds using a digital timer. After 60 seconds, the target site was wiped with another 2-inch by 2-inch cotton gauze and injecting 0.5 cartridge (0.9 mL) of 3% mepivacaine hydrochloride with no epinephrine (Henry Schein, Melville, NY) which was stored in room temperature. The needle was advanced into the tissue until it was estimated to be over the root apex while remaining parallel to the tooth's long axis. The Vibraject was activated after aspiration to deposit the solution slowly at approximately 50 seconds (time necessary to infiltrate 0.5 mL of anesthetic with the dentapen system) for both groups. The time factor was therefore limited to prevent a possible confounding effect in the patients' pain perception. Following cartridge deposition, the operator adjusted the participant to an upright

seated position so that he or she could independently record his or her perceived pain on the Visual Analogue Scale. The Vibraject was selected as the vibrator due to its simple design, battery operation, and ability to be easily attached to a syringe with minimal adjustment to conventional injection procedures. Also, compared to other vibration gadgets, it is reasonably affordable.

Figure 3: Vibraject used in the study.

Visual Analogue Scale scale

The Visual Analogue Scale score was stratified into distinct categories: "0" denoted absence of pain, scores ranging from "1-3" indicated mild pain, "4-6" signified moderate pain, "7-9" represented severe pain, and the maximum score of "10" was designated as indicative of the utmost intensity of pain conceivable.

Statistical Analysis

The statistical analysis for this study was conducted using SPSS Version 20 (IBM-SPSS Inc., Chicago, IL), a robust statistical software package that allows for detailed data management and analysis. The primary statistical tests employed were the paired T-test for analysing the heart rate data and the Wilcoxon test for the Visual Analogue Scale pain scores.

The paired T-test was chosen for the heart rate data as it is designed to compare the means of two related groups, such as the same patients' heart rates before and after each injection. This test is particularly suitable for assessing whether there is a statistically significant change in heart rate following the administration of local anaesthesia.

For the Visual Analogue Scale pain scores, the Wilcoxon test was utilized. This non-parametric test is ideal for data that are not normally distributed and is used for comparing two related samples, matched samples, or repeated measurements on a single sample. In this study, it was employed to evaluate the differences in pain scores between the two different injection techniques on the same patients.

A p-value of 0.05 or less was considered statistically significant. This conventional threshold indicates that there is only a 5% likelihood that the observed differences occurred by chance. Thus, if the p-value is less than or equal to 0.05, the results are deemed statistically significant, suggesting a real difference between the two techniques that is not due to random variation.

RESULTS

Table 1 shows the demographic characteristics of the study population, offering insights into both age and gender distribution. The mean and standard deviation for age provides a central tendency and variability measure, while the gender distribution details the proportion of males and females in the sample. The mean age of the patients was 36.1 (SD 9.33) years, with the majority being males (87.5%).

Table 1: Descriptive statistics of study participants (N=40), highlighting age and gender distribution

Study variables	N (%)
Age in years (mean \pm SD)	36.1 \pm 9.33
Gender	
• Male	35 (87.5%)
• Female	05 (12.5%)

Figure 4 presents the study population's preferred method for injecting anaesthesia. The highest number of the participants showed interest in the Dentapen® method (n = 25, 62.5%) while 15 participants showed inclination towards the Vibraject method (37.5%).

[figure not shown]

Figure 4: Preferred method of injecting local anaesthesia by the study population

Table 2 demonstrates descriptive statistics related to heart rate measurements, including mean, standard deviation, and standard error of the mean for different conditions. The mean heart rate before treatment is slightly lower for Dentapen® (70.225) compared to Vibraject (70.775). The mean heart rate after treatment is higher for Dentapen® (71.75) compared to Vibraject (71.05). Both Dentapen® and Vibraject showed an increase in mean heart rate after treatment.

Table 2: Heart rate before and after the procedure

		Mean	N	Std. Deviation	Std. Error Mean
Overall	Heart rate before	70.5000	80	10.16572	1.13656
	Heart rate after	71.4000	80	9.59905	1.07321
Dentapen®	Heart rate before	70.2250	40	10.04984	1.58902
	Heart rate after	71.7500	40	9.94794	1.57291
Vibraject	Heart rate before	70.7750	40	10.40091	1.64453
	Heart rate after	71.0500	40	9.35058	1.47846

Table 3 indicates a statistically significant increase in mean heart rate measurements following Dentapen® injection ($p=0.010$). However, no significant differences were observed in the mean heart rate measurements between the overall and Vibraject before and after injection ($p>0.05$).

Table 3: Comparison of mean heart rate measurements before and after injections with Dentapen® and Vibraject

	Paired Differences					t	P-value §
	Mean	Std. Deviation	Std. Error	95% Confidence Interval of the Difference			

						Lower	Upper		
Overall	Heart rate before - Heart rate after	- .90000	4.18133	.46749	-1.83051	.03051	- 1.925	0.058	
Dentapen®	Heart rate before - Heart rate after	- 1.5250	3.56613	.56386	-2.66550	-.38450	- 2.705	0.010 **	
Vibraject	Heart rate before - Heart rate after	- .27500	4.67940	.73988	-1.77155	1.22155	-.372	0.712	

§ P-value has been calculated using paired sample t-test.

** Significant at p<0.05 level.

Table 4 depicts the mean Visual Analogue Scale score. The mean score of Vibraject (2.175) was observed higher than that of Dentapen (1.550). However, the results yielded an insignificant difference (p=0.105). The overall mean Visual Analogue Scale score was 1.863.

Table 4: Comparison of Visual Analogue Scale between Dentapen® and Vibraject

	Mean	N	Std. Deviation	Std. Error Mean	P-value §
Overall	1.863	80	1.605	0.179	
Dentapen®	1.550	40	1.467	0.232	0.105
Vibraject	2.175	40	1.693	0.268	

§ P-value has been calculated using Mann Whitney Z-test.

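### The Sample Size sentence contradicts itself on the number of participants (40 patients with two injections each, not 40 in each of two groups), and the 80 injections are treated as independent in the 'Overall' row of Table 3

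*Combined protocol and SAP*

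**What the plan says.** The Sample Size section names the G-power calculator and reports the resulting decision to "allocate 40 participants to each of the two groups, with each participant receiving two different injections, thereby evaluating 80 sites in total". The next sentence justifies this "as each patient served as their control". The section gives no endpoint, effect size, standard deviation, power, test family or dropout allowance.

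The rest of the document describes one set of patients measured under both techniques:

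- Study Design: "This study design is a split mouth clinical trial which allowed for a within-subjects comparison".
- Steps of the Experiment, Step III: "each patient was given local anaesthesia twice, once with the Dentapen system (ramp-up mode) and once with Vibraject".
- Results, Table 1: "Descriptive statistics of study participants (N=40), highlighting age and gender distribution", made up of 35 men and 5 women.
- Results, text on Figure 4: 25 patients preferred the Dentapen, "while 15 participants showed inclination towards the Vibraject method (37.5"%).
- Results, Tables 2 and 4: 40 observations per device and 80 overall, for example the row "Heart rate before 70.5000 80 10.16572 1.13656" in Table 2, where 80 is the N.

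**The concern.** The sentence assigns 40 participants to each of two groups and two injections to every participant, yet totals 80 sites. These three statements cannot all be true of different people. The slip is not absurd on its face: Step II randomises which device comes first, which creates two order groups, so 40 in each group could be read as 80 people in two sequences. The reader has to go to the results to rule that out.

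Two things are at stake. First, the sample size is a figure the trial relies on, and with no inputs reported the reader cannot tell what effect 40 was meant to detect. That matters for reading the non-significant pain comparison (p=0.105). Second, the independent unit is the patient (40), not the injection site (80). If the two are confused in the plan, they can be confused in the analysis, and in one row of Table 3 they are.

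**Working it through.** **1. Site count.** Inputs are from the Sample Size section and Step III.

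- Literal reading: 40 participants × 2 groups × 2 injections = 160 sites. This does not match 80.
- Split-mouth reading: 40 patients × 2 injections = 80 sites, 40 per device. This matches exactly.

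The second reading agrees with the results: 35 + 5 = 40 people, 25 + 15 = 40 preferences, and 40 + 40 = 80 observations in Tables 2 and 4.

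**2. Can the 40 be re-derived?** No, because no inputs are given. Under my assumption of two-sided alpha 0.05, the standardised effects that 40 detects with t-tests are:

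| Power | 40 pairs (dz) | 40 per independent arm (d) |
|---|---|---|
| 80% | 0.454 | 0.634 |
| 90% | 0.526 | 0.734 |
| 95% | 0.585 | 0.816 |

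Here dz is the mean paired difference divided by the standard deviation of the paired differences. For the Wilcoxon signed-rank test, taking an efficiency of 0.955 relative to the t-test, the 80% figure is 0.454/√0.955 = 0.465.

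Round-number inputs lead to about 40 in either family. A dz of 0.6 at 95% power needs 39 pairs (40 with the Wilcoxon adjustment). A d of 0.65 at 80% power needs 38 to 39 per arm, depending on whether the normal or the t formula is used. The figure 40 therefore does not identify the test used for sizing.

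**3. Does the 80 enter an analysis as independent units?** Inputs are from Table 3, 'Overall' row: mean difference -0.90000, SD 4.18133, SE 0.46749, interval -1.83051 to 0.03051.

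- SE: 4.18133/√80 = 0.4675, the printed value.
- Half-width of the interval: (0.03051 + 1.83051)/2 = 0.93051.
- Multiplier: 0.93051/0.46749 = 1.990, which is the 97.5% point of t with 79 degrees of freedom.

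The row therefore counts two injections in the same patient as two independent observations. There are only 40 patients, so a patient-level analysis has 39 degrees of freedom.

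**4. How much could that matter?** Averaging the two changes within a patient leaves the mean at -0.90. With the device SDs in Table 3 (3.56613 and 4.67940), the variance of the patient-level mean is (3.56613² + 4.67940² + 2r × 3.56613 × 4.67940)/4, where r is the unreported correlation between a patient's two changes. Dividing by 40 and taking the square root gives the SE.

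| Assumed r | SE | t magnitude (39 df) | p |
|---|---|---|---|
| -0.3 | 0.392 | 2.295 | 0.027 |
| 0 | 0.465 | 1.935 | 0.060 |
| 0.3 | 0.528 | 1.704 | 0.096 |
| 0.5 | 0.566 | 1.589 | 0.120 |

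The printed result is t = -1.925, p = 0.058. With r at zero the patient-level answer is nearly the same. With positive r the printed interval is too narrow, and with negative r it is too wide.

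**The case against.** The strongest defence is that this is a wording slip. The document uses groups for conditions within the same people: Statistical Analysis describes the paired t-test as comparing two related groups, and the Vibraject section sets the injection time for both groups, meaning both devices. On that usage the two groups are the two techniques, with 40 sites each from the same 40 patients, and only the word participants is wrong. This stands as an explanation of how the sentence arose. It does not remove the need to correct it.

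Two stronger readings are tempting, and the documents support neither.

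- *The stated size describes a parallel-group trial that was not run.* The same sentence gives every participant both injections, and the next calls each patient their own control. No G-power test family is stated. The footnote to Table 4 names a Mann-Whitney test although Statistical Analysis plans a Wilcoxon test for related samples. That raises the question of a two-sample framing, but it concerns how the results were analysed, not how the trial was sized.
- *The trial ran at half its required size.* This needs a requirement of 80 people, which is stated nowhere and conflicts with the 80-site total.

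Nor would a two-sample calculation by itself show harm. For d = 0.634, dz = d/√(2(1 - r)), with r here the within-patient correlation of the outcome. The power of 40 pairs is then 79.0%, 91.1% and 97.4% at r = 0, 0.3 and 0.5.

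It is also fair to say that the document calls the 80 sites and never calls them independent units, and that the 'Overall' row is an analysis defect which rewording the sentence would not cure. Both are true, so the row needs its own correction.

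**Conclusion.** The concern holds in a limited form. The Sample Size sentence is internally inconsistent by a factor of two: 160 sites as worded against 80 as stated. The evidence for 40 patients and 80 sites is consistent throughout the rest of the document. Whether the calculation behind the 40 was paired or two-sample cannot be determined, so no claim about under- or over-sizing follows.

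The consequence that can be demonstrated is confined to the 'Overall' row of Table 3, which uses 79 degrees of freedom where 40 patients supply 39. The direction and size of the error there depend on a correlation the documents do not report. The device-specific rows, with N = 40 each, are unaffected by this point. The detectable effects rest on an assumed two-sided alpha of 0.05: the document gives 0.05 as its significance threshold, but neither as a sizing input nor with sidedness.

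**What to change.** 1. Restate the sentence as: 40 patients, each receiving both techniques once (40 within-patient pairs, 80 injection sites).
2. Report the original G-power inputs: endpoint, test family, alpha and sidedness, power, effect size with the standard deviation it rests on, and any dropout allowance.
3. If those cannot be recovered, say so and give the detectable paired effect for 40 pairs: dz about 0.45 at 80% power and 0.53 at 90% with a paired t-test, and about 0.465 at 80% with the Wilcoxon signed-rank test. Label it a retrospective sensitivity figure with the alpha assumption stated. The trial is complete, so a new G-power run cannot serve as justification for the original size.
4. Do not use 80 as a number of independent units. Drop the 'Overall' row of Table 3, or re-analyse it on 40 patient-level mean changes (39 degrees of freedom) or with a model that accounts for patient.

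The cost is one rewritten sentence, a look at the original G-power record, and one short re-analysis or a deleted row. No extra patients are needed. The drawback for the sponsor is that the stated figures may look slightly less favourable.

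### The order of the post-injection heart rate and pain score is stated in two conflicting ways, and posture and timing of the heart-rate readings are not given, so the within-device before-after test cannot isolate the injection.

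*Combined protocol and SAP*

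**What the plan says.** For the first injection, Study Design has heart rate measured again after the injection, "then the patient will be asked to evaluate pain intensity with Visual Analogue Scale". For the second, it says that "heart rate was measured once more to capture the immediate physiological response and the patient will be asked again to evaluate pain intensity". Both sentences name heart rate before pain. Only the first fixes the sequence, because the second joins the two measurements with a plain conjunction.

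Steps of the Experiment has the reverse. It reads "Step IV: Immediately after each local anaesthesia injection operation, the patient was asked to use the Visual Analogue Scale", followed by "Step V: After administering a local anaesthetic, the patient's heart rate was measured with a pulse oximeter". Step V gives no interval.

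The Dentapen section says that after deposition "the operator adjusted the participant to an upright seated position so that he or she could independently record" the pain score, and the Vibraject section says the same. The move upright therefore comes before scoring with both devices.

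No section states the patient's position at the pre-injection or post-injection heart-rate reading.

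Statistical Analysis plans a paired t-test of heart rate before against after each injection. Above Table 3, the Results report a "statistically significant increase in mean heart rate measurements following" Dentapen injection (p = 0.010).

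**The concern.** A before-after test attributes to the injection whatever changed between the two readings. Here the move upright and the act of scoring fall in that interval under one stated order, and may fall outside it under the other. If position or delay differed between the readings, the paired difference mixes their effect with that of the injection.

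A disturbance common to both devices would cancel if the changes were compared between devices. The reported heart-rate tests compare before with after, within each device and overall, so nothing cancels in them. At stake is the interpretation of the only p-value in the Results at or below 0.05.

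**Working it through.** **Inputs (Table 3, signs reversed so that a rise is positive).** Dentapen: mean change 1.525, SD 3.56613, n = 40. Vibraject: mean change 0.275, SD 4.67940, n = 40. The significance threshold is 0.05 (Statistical Analysis). Sidedness is not stated, but the reported p-values match two-sided tests.

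**Step 1: reproduce the reported result.**
- Dentapen: SE = 3.56613/√40 = 0.5639; t = 1.525/0.5639 = 2.705 on 39 df; p = 0.010; 95% CI = 1.525 ± 2.023 × 0.5639 = 0.384 to 2.666.
- Vibraject: SE = 4.67940/√40 = 0.7399; t = 0.372; p = 0.712; 95% CI −1.22 to 1.77.

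Both agree with Table 3.

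**Step 2: sensitivity to a non-injection shift.** Let *s* be a rise due to position or delay, equal for both devices. The documents give no value, so every *s* here is an assumption. Then net change = observed change − *s*, and t = net change/SE.

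| Assumed *s* | Dentapen net | p | Vibraject net | p |
|---|---|---|---|---|
| 0 | 1.525 | 0.010 | 0.275 | 0.71 |
| 0.25 | 1.275 | 0.029 | 0.025 | 0.97 |
| 0.3845 | 1.14 | 0.050 | −0.11 | 0.88 |
| 0.5 | 1.025 | 0.077 | −0.225 | 0.76 |
| 1.0 | 0.525 | 0.36 | −0.725 | 0.33 |
| 1.525 | 0 | 1.00 | −1.25 | 0.099 |

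The Dentapen result loses significance once *s* exceeds the lower confidence limit of 0.3845. To explain the whole Dentapen rise, *s* must be 1.525. The Vibraject injection would then have had to lower heart rate by 1.25.

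**Step 3: the contrast in which a shared shift cancels.** The between-device difference in change is 1.525 − 0.275 = 1.25 beats/min. Its SD is √(3.56613² + 4.67940² − 2·r·3.56613·4.67940), where r is the within-patient correlation of the two changes. The documents do not report r, so a range is assumed, with n = 40 and 39 df.

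| Assumed r | SD | t | p | 95% CI |
|---|---|---|---|---|
| −0.3 | 6.680 | 1.183 | 0.24 | −0.89 to 3.39 |
| 0 | 5.883 | 1.344 | 0.19 | −0.63 to 3.13 |
| 0.3 | 4.960 | 1.594 | 0.12 | −0.34 to 2.84 |
| 0.5 | 4.234 | 1.867 | 0.069 | −0.10 to 2.60 |
| 0.7 | 3.354 | 2.357 | 0.024 | 0.18 to 2.32 |

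The contrast reaches p ≤ 0.05 only if r is about 0.58 or more. No such test is reported.

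**The case against.** The numbered steps are not strictly chronological. Step III is already the second injection, while Step IV applies after each one. Step V does not say that heart rate follows scoring. Steps IV and V could therefore be a list of measurements compatible with the Study Design order, and the stated aim of catching an immediate response favours an early reading. The flow chart, which is not reproduced in the text available here, may settle the order. This softens the conflict but does not remove it: the section introduces its steps as a sequence, and a reader following it would score pain first.

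The posture argument is also partly inferred. A reclined baseline is suggested only by the later move upright. Study Design takes the baseline ahead of any procedure, so the patient may have been upright then. In that case the Steps order would give matched positions, and any mismatch would arise under the other order. This stands, and it means that neither the presence nor the direction of a shift can be asserted.

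The 0.4 beats/min figure is the lower confidence limit restated, and it would apply to any disturbance of this test. That is correct. It shows how little margin the result has and is not evidence of bias.

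Finally, heart rate is introduced as an addition to the pain score, and the Results sentence above Table 3 claims only a rise following the injection, not a difference between devices. This limits the consequence to the heart-rate interpretation.

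**Conclusion.** The point holds as an unresolved inconsistency that limits what the heart-rate test can show. The sections conflict on order, the move upright lies between deposition and scoring, and position and timing of the readings are unstated. The Dentapen p of 0.010 is a correct calculation, but it cannot be attributed to the injection alone until those facts are given. An assumed upward shift of about 0.4 beats/min would be enough to lose significance; a downward shift would mean that the rise is understated.

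A reader might infer three stronger conclusions that the documents do not support:
- **That posture produced the Dentapen rise.** The same upright wording applies to Vibraject, whose change was 0.275. A shared shift of 1.525 lies inside the Vibraject interval (−1.22 to 1.77), so it is not excluded, but the point estimate argues against it.
- **That the order varied between patients.** Risk of Bias describes one trained operator working to one procedure, and nothing suggests such variation.
- **That the pain or preference results are compromised.** They do not use the heart-rate readings, and the move upright before scoring is the same for both devices.

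Cancellation in the between-device contrast assumes that the order and positions were the same for both devices.

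**What to change.** Reconcile Study Design, Steps of the Experiment and the two injection sections to one order. State that both heart-rate readings are taken in the same position, whichever it is, and that the second is taken at a fixed time after the end of deposition.

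For the data already collected, report the order, position and timing actually used. If these differed between the readings or were not recorded, do not read the within-device before-after p-values as effects of the injection. Report instead the paired between-device comparison of heart-rate changes, with its confidence interval.

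The protocol change is wording only, and the contrast needs no new measurement. The cost is in the claim: the Dentapen p = 0.010 would support less, and the contrast may well not be significant, depending on the correlation that the patient-level data would supply.
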